#### 8.4.2 Colitis

In study CA216001, DLTs consisting of Grade 3 colonic ulceration/Grade 3 diarrhea were reported, both indicating the potential for development of colitis. Intestinal inflammation is thought to be an on-target effect that requires close monitoring and potential dose reductions. Intense abdominal pain, severe diarrhea and the presence of blood and/or mucous in the stools are indicative of potential colitis. Signs and symptom of colitis should prompt work up to rule out an infectious etiology. The gold standard for the diagnosis of colitis pathological and thus requires a biopsy, but in the absence of an infectious etiology, colitis should be the exclusion diagnosis. For management of colitis see Table 10.

**Table 10** **Colitis Management**

Grade	Dose Modification	Management
Any Grade		
 
Patients should be thoroughly evaluated to rule out any alternative etiology (e.g., disease progression, other medications, infections including testing for clostridium difficile toxin, etc.)
 
Steroids should be considered in the absence of clear alternative etiology, even for low grade events, in order to prevent potential progression to higher grade event
 
 
Use analgesics carefully; they can mask symptoms of perforation and peritonitis

Grade 1	No dose modification	Actively monitor frequency, consistency and appearance of stools (especially for presence of mucus or blood) and for the emergence of abdominal pain or cramps
Grade 2	If on AL101 6 mg QW: change dose regimen to 6 mg 2 weeks on / 1 week off for the first episode.  Decrease AL101 dose to 4 mg QW for second episode and	
 
Promptly start prednisone 1 to 2 mg/kg/day or IV equivalent
 
If event is not responsive within 3-5 days or worsens despite prednisone at 1-2 mg/kg/day or IV equivalent, GI consult should be obtained for consideration of further workup such as imaging and/or colonoscopy to confirm colitis and rule out perforation and prompt treatment with IV methylprednisolone 2- 4mg/kg/day started.
 
Caution: Important to rule out bowel perforation
 

Confidential

Document State: Effective (Controlled)  
CONFIDENTIAL

Page 76 of 118

Grade	Dose Modification	Management
	to 2.4 mg QW for third episode. If on AL101 4 mg QW: decrease dose to 2.4 mg QW	
 
Consult study physician if no resolution to <math>\leq</math> Grade 1 in 3-4 days
 
 
Once improving, gradually taper steroids over <math>\geq</math>28 days and consider prophylactic antibiotics, antifungals and anti PCP treatment (please refer to current NCCN guidelines for treatment of cancer-related infections [Category 2B recommendation])

Grade 3-4	Permanently discontinue investigational product	
 
Promptly initiate empiric IV methylprednisolone 2 to 4 mg/kg/day or equivalent
 
Monitor stool frequency and volume and maintain hydration
 
Urgent GI consult and imaging and/or colonoscopy as appropriate
 
 
Caution: Ensure GI consult to rule out bowel perforation
 
Once improving, gradually taper steroids over <math>\geq</math>28 days and consider prophylactic antibiotics, antifungals and anti PCP treatment (please refer to current NCCN guidelines for treatment of cancer-related infections [Category 2B recommendation])

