	
improvement within 3 days with maximum doses of loperamide:
 
 
• Patient may be treated with dexamethasone at a dose of 8 mg every 8 hours (Q8h) for up to 5 days. If still no improvement in symptoms, the patient may continue with the dexamethasone or consider switching to budesonide 9 mg once daily (QD). Refer to Section 7.1.2 for additional instructions on premedication with steroids.
 
 
Dose modifications for AL101:
 
Interrupt AL101 until resolution to <math>\leq</math> Grade 1 (refer to Section 7.1.2 for management guidelines for diarrhea and above for management guidelines for diarrhea).
 
Decrease AL101 dose to 2.4 mg QW.
 
If the diarrhea does not resolve to Grade 1 by 14 days, the patient will be discontinued from AL101 (refer to Section 4.5 for early withdrawal of patients from therapy or assessment).
 
If treatment interruption is longer than 28 days, the patient will be discontinued from AL101 (refer to Section 4.5 for early withdrawal of patients from therapy or assessment).
	
improvement within 3 days with maximum doses of loperamide:
 
 
• Patient may be treated with dexamethasone at a dose of 8 mg Q8h for up to 5 days. If still no improvement in symptoms, the patient may continue with the dexamethasone or consider switching to budesonide 9 mg QD. Refer to Section 7.1.2 for additional instructions on premedication with steroids.
 
 
Dose modifications for AL101:
 
Interrupt AL101 until resolution to <math>\leq</math> Grade 1 (refer to Section 7.1.2 and above for management guidelines for diarrhea).
 
Change dose regimen to 6 mg 2 weeks on / 1 week off for first episode
 
Decrease AL101 dose to 4 mg QW for second episode and to 2.4 mg QW for third episode.
 
If the diarrhea does not resolve to Grade 1 by 14 days, the patient will be discontinued from AL101 (refer to Section 4.5 for early withdrawal of patients from therapy or assessment).
 
If treatment interruption is longer than 28 days, the patient will be discontinued from AL101 (refer to Section 4.5 for early withdrawal of patients from therapy or assessment).

Grade 3 diarrhea	Guidelines for the management of diarrhea:	Guidelines for the management of diarrhea:

Confidential

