Confidential

 Document State: Effective (Controlled)  
 CONFIDENTIAL

Page 56 of 118

Dose Modification Criteria for AL101 -Related Adverse Events	AL101 modification	
	Note: for any questions, please contact the Sponsor's Medical Monitor.	
	Cohort 1 (4 mg QW IV)	Cohort 2 (6 mg QW IV)
	
Interrupt AL101 until resolution to <math>\leq</math> Grade 1 (refer to Section 6.6.2 and above for management guidelines for diarrhea).
 
Decrease AL101 dose to 2.4 mg QW.
 
If the diarrhea does not resolve to Grade 1 by 14 days, the patient will be discontinued from AL101 (refer to Section 4.5 for early withdrawal of patients from therapy or assessment).
 
If treatment interruption is longer than 28 days, the patient will be discontinued from AL101 (refer to Section 4.5 for early withdrawal of patients from therapy or assessment).
	
Interrupt AL101 until resolution to <math>\leq</math> Grade 1 (refer to Section 7.1.2 and above for management guidelines for diarrhea).
 
Change dose regimen to 6 mg 2 weeks on / 1 week off for the first episode.
 
Decrease AL101 dose to 4 mg QW for second episode and to 2.4 mg QW for third episode
 
If the diarrhea does not resolve to Grade 1 by 14 days, the patient will be discontinued from AL101 (refer to Section 4.5 for early withdrawal of patients from therapy or assessment).
 
If treatment interruption is longer than 28 days, the patient will be discontinued from AL101 (refer to Section 4.5 for early withdrawal of patients from therapy or assessment).

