	
 
For patients that cannot tolerate loperamide or do not get adequate relief with maximum doses, standard doses of LOMOTIL® (diphenoxylate/atropine) may be added or used instead of loperamide.
 
Additional antidiarrheal measures, such as octreotide, may be used at the discretion of the investigator or treating physician
 
Treat with dexamethasone at a dose of 8 mg every Q8h for up to 5 days. If still no improvement in symptoms, the patient may continue with the dexamethasone or consider switching to budesonide 9 mg QD. Refer to Section 7.1.2 for additional instructions on premedication with steroids.
 
 
If the above measures have not worked, or patient has progressed to Grade 4, consult GI as necessary to evaluate for colitis.
 
Dose modifications for AL101:
 
Permanently discontinue AL101 (refer to Section 4.5 for early withdrawal of patients from therapy or assessment).
	
standard doses of LOMOTIL® (diphenoxylate/atropine) may be added or used instead of loperamide.
 
 
Additional antidiarrheal measures, such as octreotide, may be used at the discretion of the investigator or treating physician
 
Treat with dexamethasone at a dose of 8 mg Q8h for up to 5 days. If still no improvement in symptoms, the patient may continue with the dexamethasone or consider switching to budesonide 9 mg QD. Refer to Section 7.1.2 for additional instructions on premedication with steroids.
 
 
If the above measures have not worked, or patient has progressed to Grade 4, consult GI as necessary to evaluate for colitis.
 
Dose modifications for AL101:
 
Permanently discontinue AL101 (refer to Section 4.5 for early withdrawal of patients from therapy or assessment).

Diagnosed or suspected clinically significant gastrointestinal (GI) bleeding or unexplained drop in hemoglobin	
Interrupt AL101, perform appropriate diagnosis and treatment.
 
If GI bleeding is considered related to AL101 reduce 1 dose level to 2.4 mg QW.
	
Interrupt AL101, perform appropriate diagnosis and treatment.
 
If GI bleeding is considered related to AL101, Decrease to 4 mg QW for first episode and to 2.4 mg QW for second episode 1 dose level.

Confidential

 Document State: Effective (Controlled)  
 CONFIDENTIAL

Page 58 of 118

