Dose Modification Criteria for AL101 -Related Adverse Events	AL101 modification	
	Note: for any questions, please contact the Sponsor's Medical Monitor.	
	Cohort 1 (4 mg QW IV)	Cohort 2 (6 mg QW IV)
	
If colitis is suspected please refer to Section 8.4.2, Table 10 for management guidelines for colitis.
 
If treatment interruption is longer than 28 days, the patient will be discontinued from the study.
	
If colitis is suspected please refer to Section 8.4.2, Table 10 for management guidelines for colitis.
 
If treatment interruption is longer than 28 days, the patient will be discontinued from the study.

Grade 3 or 4 gastric hemorrhage	
Permanently discontinue AL101 (refer to Section 4.5 for early withdrawal of patients from therapy or assessment).
	
Permanently discontinue AL101 (refer to Section 4.5 for early withdrawal of patients from therapy or assessment).

QTcF > 500 msec confirmed by at least one repeat ECG and at least 50 msec above baseline	
Interrupt if needed to optimize electrolyte management. If persists after electrolyte optimization (including dose modification of AL101 if necessary), discontinue.
 
If treatment interruption is longer than 28 days, the patient will be discontinued from the study.
	
Interrupt if needed to optimize electrolyte management. If persists after electrolyte optimization (including dose modification of AL101 if necessary), discontinue.
 
If treatment interruption is longer than 28 days, the patient will be discontinued from the study.

AST or ALT > 5 times the institutional ULN	
Interrupt AL101 until resolution to <math>\leq</math> Grade 1 and then resume at 1 dose level lower (i.e., 2.4 mg QW). Refer to Section 8.4.1 for hepatic function abnormalities and Section 8.4.5 for drug-induced liver toxicity management.
 
If treatment interruption is longer than 28 days, the patient will be discontinued from the study.
	
Interrupt AL101 until resolution to <math>\leq</math> Grade 1 and then decrease dose to 4 mg QW for first episode and to 2.4 mg QW for second episode.
 
Refer to Section 8.4.1 for hepatic function abnormalities and Section 8.4.5 for drug-induced liver toxicity management.
 
If treatment interruption is longer than 28 days, the patient will be discontinued from the study.

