Any other AL101-related Grade 3 nonhematologic adverse event except electrolyte abnormalities that may be managed with supplements	Interrupt AL101 until resolution to $\leq$ Grade 1 and then resume at 1 dose level lower (i.e., 2.4 mg QW). If treatment interruption is longer than 28 days, the patient will be discontinued from the study (refer to Section 4.5 for early withdrawal of patients from therapy or assessment).	Interrupt AL101 until resolution to $\leq$ Grade 1 and then change dose regimen to 6 mg 2 weeks on / 1 week off for the first episode. Decrease dose to 4 mg QW for second episode and to 2.4 mg QW for third episode. If treatment interruption is longer than 28 days, the patient will be discontinued from the study (refer to Section 4.5 for early withdrawal of patients from therapy or assessment).

Confidential

 Document State: Effective (Controlled)  
 CONFIDENTIAL

Page 60 of 118

Dose Modification Criteria for AL101 -Related Adverse Events	AL101 modification	
	Note: for any questions, please contact the Sponsor's Medical Monitor.	
	Cohort 1 (4 mg QW IV)	Cohort 2 (6 mg QW IV)
Grade 4 non-hematologic AEs including Grade 4 non-hematologic lab abnormalities lasting > 72 hours	Permanently discontinue from IP (refer to Section 4.5 for early withdrawal of patients from therapy or assessment ).	Permanently discontinue from IP (refer to Section 4.5 for early withdrawal of patients from therapy or assessment ).

Confidential

 Document State: Effective (Controlled)  
 CONFIDENTIAL

Page 61 of 118

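### The Grade 2 colitis row of Table 10 changes the AL101 regimen or dose without first holding the drug, so a narrow group of patients may be infused while colitis is active

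*Protocol*

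**What the plan says.** Protocol Section 8.4.2, Table 10, sets the colitis rules. For Grade 2 the dose cell reads "If on AL101 6 mg QW: change dose regimen to 6 mg 2 weeks on / 1 week off for the first episode". A second episode goes to 4 mg weekly and a third to 2.4 mg weekly; a patient on 4 mg weekly goes to 2.4 mg. The cell does not suspend dosing and does not say how far the colitis must settle before the next infusion.

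The management cell of the same row starts prednisone at 1-2 mg/kg/day. It moves to a GI consult and IV methylprednisolone if there is no response in 3-5 days, and tapers steroids over at least 28 days. Its one reference to resolution is "Consult study physician if no resolution to" Grade 1 or lower in 3-4 days. Grade 3-4 colitis ends AL101 permanently.

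Table 6 in Section 6.6 handles Grade 2 diarrhea differently. In both cohorts it begins "Interrupt AL101 until resolution to" Grade 1 or lower. Cohort 2 then has "Change dose regimen to 6 mg 2 weeks on / 1 week off for first episode", and Cohort 1 goes to 2.4 mg. If the diarrhea has not reached Grade 1 by 14 days, AL101 is discontinued. The Amendment 3 summary of changes shows that the 2-on/1-off step was introduced for Grade 2-3 diarrhea and Grade 2 colitis together.

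**The concern.** Colitis is a named adverse event of special interest, and Section 8.4.2 regards intestinal inflammation as on-target. Section 6.6.2 explains its hold for uncontrolled Grade 2 or higher diarrhea in two ways: further dosing would probably make the event worse, and the gut probably takes longer to recover than the symptom takes to clear. That reasoning is written for diarrhea, but it applies naturally to colitis.

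The drug also persists. Section 1.3.2 gives mean half-lives of 67.4 to 147.8 hours, which is 67.4/24 = 2.8 to 147.8/24 = 6.2 days. An infusion given during active colitis therefore stays in the body for days. One grade higher, the patient loses the drug for good. At stake is patient safety during an episode; sample size, power, type I error and the primary analysis are not affected.

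**Working it through.** The plan has no figure of its own to reproduce on this point. The check sets the rules side by side.

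**1. Rules that could hold AL101 during Grade 2 colitis**
- Section 8.4 sends dose changes for events of special interest to Section 6.6. Table 6 there has no colitis row, and its GI-bleeding row refers suspected colitis back to Table 10.
- That bleeding row begins "Interrupt AL101, perform appropriate diagnosis and treatment". It covers clinically significant bleeding, confirmed or only suspected, and an unexplained fall in hemoglobin.
- The Table 6 diarrhea rows hold AL101 at Grades 2 and 3 and discontinue it at Grade 4.
- The Table 6 catch-all row for other nonhematologic events covers Grade 3 only.
- Section 4.5 requires a hold for serious related reactions only.
- Section 6.6 leaves intolerable Grade 2 toxicity to case-by-case review with the Sponsor.
- Section 7.1.4 prohibits chronic glucocorticoids above 10 mg/day prednisone equivalent. It does not define chronic, and Table 10 itself prescribes the steroids, so this is not a clear hold.
- Reporting of these events within 24 hours (Table 7), Sponsor discussion of immediate safety concerns (Section 5) and pre-infusion assessments (Schedule of Activities notes) are safeguards, but none requires a hold.

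**2. What is left uncovered**

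Non-serious Grade 2 colitis with at most Grade 1 diarrhea, no confirmed or suspected significant bleed and no unexplained hemoglobin drop. Section 8.4.2 lists intense abdominal pain and mucus in the stool among the signs of colitis, and neither triggers a hold by itself.

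**3. Comparators**

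Only Grade 2 diarrhea matches on grade, organ system and amendment. The other two Cohort 2 rows with the 2-on/1-off step ("Change dose regimen to 6 mg 2 weeks on / 1 week off for the first episode" for Grade 3 diarrhea, "then change dose regimen to 6 mg 2 weeks on / 1 week off for the first episode" for other Grade 3 events) also interrupt first, but at a higher grade.

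**4. Does the consult trigger come before the next infusion?**

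Let colitis begin d days after an infusion. The next infusion is nominally due at day 7, and the trigger falls at day d+3 to d+4.
- For d = 3 or less, d+4 is at most 7, so the trigger falls on or before the infusion day.
- For d = 4 or more, d+3 is at least 7, so the infusion is due on or before the trigger.

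In either case the trigger calls for a consultation, not a hold.

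**5. Illustrative exposure during an active episode**

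The documents give no rate or duration for Grade 2 colitis, so episode length is assumed. Weekly slots = days/7. On the on-on-off pattern, the infusions across the three possible starting positions are {1,1,0} for 1 slot, {2,1,1} for 2 slots and {3,3,2} for 4 slots.

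| Assumed episode | Slots | 6 mg, 2 on / 1 off | 2.4 mg weekly |
|---|---|---|---|
| 7 days | 1 | 0-1 x 6 = 0-6 mg | 1 x 2.4 = 2.4 mg |
| 14 days | 2 | 1-2 x 6 = 6-12 mg | 2 x 2.4 = 4.8 mg |
| 28 days | 4 | 2-3 x 6 = 12-18 mg | 4 x 2.4 = 9.6 mg |

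The 2-on/1-off change lowers the three-week total from 3 x 6 = 18 mg to 2 x 6 = 12 mg, a cut of 6/18 = 33%. Each infusion remains 6 mg.

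**The case against.** **The regimen change may be meant for after recovery.** The Amendment 3 rationale says the scheduled break is there to prevent recurrence, and the row counts episodes, which suggests a schedule for use once an episode has settled. That is a fair reading, but the row does not state it. The off week is a calendar break that may come after one or two more 6 mg infusions, and patients on 4 mg weekly get no break.

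**The row has an escalation path.** Steroids, a physician consult at 3-4 days and a GI consult at 3-5 days are real protection. When colitis begins soon after an infusion they precede the next dose. They make long unmanaged dosing less likely, so the 14- and 28-day figures are the less plausible part of the range. They do not make a hold mandatory.

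**Colitis usually brings a trigger that does hold.** Section 8.4.2 also lists severe diarrhea and blood in the stool, and the rules for those will often apply. This stands, and it is why the point is confined to a residual group.

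**A stronger reading to resist.** A reader might infer that the colitis row is the lone exception to a general interrupt-first rule, since all three Cohort 2 rows with 2-on/1-off, and all six Cohort 1 nonhematologic step-downs to 2.4 mg, interrupt first. The documents do not support that. Most of those rows concern Grade 3 events or comparably severe triggers. The Grade 2 infusion-reaction row only premedicates, and the neutropenia and thrombocytopenia rows reduce the dose with no stated hold. The like-for-like precedent is one row.

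**Conclusion.** The omission is real. Followed as written, Table 10 permits an infusion of up to 6 mg while Grade 2 colitis is active, where the matching Grade 2 diarrhea rule would hold it. It affects only the residual group in step 2 of the working.

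A reader might conclude that the protocol directs dosing through Grade 2 colitis in general, or that the exposure figures measure expected harm. Neither follows. Many presentations are held under other rules, investigators remain free to hold, and the milligram totals rest on assumed episode lengths, with zero infusions possible at 7 days on the altered 6 mg schedule. Confidence is high about the missing text and low about how often it would matter. This is a cheap improvement to a safety rule.

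**What to change.** In the Grade 2 row of Table 10, for both dose levels, place "Interrupt AL101 until resolution to" Grade 1 or lower, followed by the word then, ahead of the regimen or dose change. Keep this within the 28-day maximum interruption in Section 6.6. Tie the hold to grade and not to the end of steroid treatment, because a taper of at least 28 days would by itself reach that maximum. State also whether the 14-day non-resolution stop in the Grade 2 diarrhea row applies to colitis.

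The cost is one edited table row and no new procedure. The downside is missed weekly doses: up to about 28/7 = 4 under the 28-day limit, or about 14/7 = 2 if the 14-day stop is adopted. For a first episode at 6 mg, the net loss under the 28-day limit is 2-3 infusions, since the remaining slots would have been off weeks.

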#### 8.4.3 Infusion Reactions including Anaphylaxis

In study CA216001 1 patient developed Grade 3 anaphylaxis, a dose limiting toxicity (DLT) at the 4 mg dose. In case of Grade 3 or 4 allergic reaction, stop investigational product infusion and disconnect infusion tubing from the patient.

For infusion reactions, refer to Section [6.6.1](#).

#### 8.4.5 Potential Drug-Induced Liver Injury (DILI) / Hy's Law

Wherever possible, timely confirmation of initial liver-related laboratory abnormalities should occur prior to the reporting of a potential DILI event. All occurrences of potential DILIs, meeting the defined criteria, must be reported as SAEs (see Section 8.5 for reporting details). The criteria for identifying p-DILI events depend on whether the patient's baseline liver biochemistry is normal or abnormal (see Figure 2).

**Figure 2** **Algorithm for p-DILI identification and mandatory SAE reporting in patients with - (i) normal baseline liver biochemistry, and (ii) abnormal baseline liver biochemistry.**

The key responsibilities for investigators during p-DILI assessment include: (i) Early detection, medical evaluation (including the exclusion of other potential causes) and rapid laboratory confirmation of liver-related abnormalities, and (ii) Sponsor notification of p-DILI cases via SAE forms. Following the gathering and assessment of relevant clinical information the Sponsor is responsible for: (iii) Timely evaluation and triaging of p-DILI cases, (iv) Expedited reporting of p-DILI cases and (v) Expanded review of p-DILI cases including a detailed assessment of all available clinical information, investigations and biochemical data.

Investigators are expected to monitor ongoing routine and ad hoc hepatic laboratory test results to rapidly determine whether a patient meets p-DILI criteria. They are expected to promptly notify the Sponsor/Medical Monitor of all p-DILI cases. p-DILI cases may be identified by abnormal liver biochemistry values, whether or not they are accompanied by liver-related signs

and/or symptoms. In both cases, expedited confirmation with repeat laboratory testing should occur within 3 business days using a Hepatic Laboratory Panel (ALT, AST, TB, AP). Any patient with an abnormal Hepatic Laboratory Panel that meets p-DILI criteria (see [Figure 2](#)) is a candidate for investigational product discontinuation. Any confirmed p-DILI events must be reported (along with a description of the clinical findings) to Sponsor as an SAE within 24 hours of confirmation.

An extensive clinical history, examination and appropriate investigations should be obtained to exclude cholestatic and other apparent causes that may explain the observed abnormalities in liver function and/or hepatic signs and symptoms. Other apparent causes include, non-exhaustively and by way of example only: infectious diseases (such as active hepatitis -A, -B and -C), congenital diseases (such as Gilbert's syndrome), neoplastic diseases (such as hepatocellular carcinoma), autoimmune diseases (such as primary biliary cirrhosis) and the use of concomitant hepatotoxic medications (such as antibiotics, the oral contraceptive pill and herbal medicines). All investigations to exclude potential causes of liver function abnormalities or hepatic signs and/or symptoms should be guided by relevant factors such as the patient's age, gender, clinical history, and signs and symptoms.

